## 5 Study Methods

### 5.1 General Study Design and Plan

We will conduct a 36-week pragmatic trial in a cohort of cLBP patients (see Figure 1 and Figure 2). The proposed SMART will consist of a 4-week run-in period using an online cognitive-behavioral self-management intervention (PainGuide), followed by two 8-week treatment periods. All participants will be followed for a total of approximately nine months.

At baseline (T1), approximately 500 patients will undergo a comprehensive baseline phenotyping assessment. After receiving PainGuide (access to an online self-management program) for 4 weeks, each participant will complete a light phenotyping assessment (T2) and a subset of these patients (n=160) will complete an additional deep phenotyping assessment. Those who still have significant pain interference ( $\geq 2$  from Patient Global Impression Scale, PGIC) will be randomized to one of the four 8-week long interventions (i.e., Mindfulness-Based Stress Reduction (MBSR), Physical Therapy (PT)/Exercise, Acupressure self-management [eHealth app], or Duloxetine). Participants with a PGIC=1 will not be randomized and continue with long-term follow-up. The PainGuide run-in is designed to provide the lightest “touch” intervention and to help control for regression to the mean. We will use block randomization with random block size of 4 and 8. Approximately 102 patients will be assigned to each treatment group including Physical Therapy/Exercise, MBSR, Acupressure, and Duloxetine treatment groups. For addition details, please see Section 6.3.

Following the first 8-week treatment period, patients will be reassessed (T3) using light only or light plus deep assessments (for the subset of 160) and those still having significant pain interference ( $\geq 2$  from Patient Global Impression Scale [PGIC]) will be re-randomized to receive one of the three treatments they did not receive in the first treatment period. Participants with a PGIC=1 will not be randomized and continue with long-term follow-up. After the second intervention and three months later, all undergo the light phenotyping follow-up assessment protocol (T4). Lastly, a final assessment will take place at 3 months after the scheduled end of the second 8-week treatment period (T5). There will also be a series of interim assessments that take place at 2-week intervals in between the regular assessments (T1-T5).

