#### **5.4.2 Inclusion Criteria for Light Phenotyping**

- We will use the definition of chronic low back pain (cLBP) described in the NIH Task Force Report on Research Standards for Chronic Low Back Pain, i.e. low back pain present at least six months, and present more than half of those days.
- Individuals must have a pain interference score of  $\geq 60$  on PROMIS Pain Interference at T1 for inclusion. The normal population mean and standard deviation for the PROMIS Pain Interference measures are 50 and 10 points, respectively. Therefore, participants must be 1 SD above the population mean ( $>=60$ ) for inclusion.
- Individuals must be willing and eligible to be randomized to receive at least three of the four proposed treatments.

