### **5.5 Randomization and Blinding**

Blocked randomization will be used for the randomization schedule. Block size will be randomized between 4 and 8 and the ordering of treatment assignments within a block will be random.

Randomization will be performed without stratification. Study recruitment will continue until 408 patients have been randomized into a treatment group at study phase T2. We expect that it will be necessary to recruit approximately 500 patients into the study in order to achieve the target of 408 SMART participants. Based on our previous studies , we expect that approximately 15-20% of patients recruited at study phase T1 will not enter the SMART at study phase 2 due to either response to the PainGuide self-management intervention or withdrawal from the study.

We will perform randomization using a randomization software or a randomization list created by a statistician to assign participants to a treatment in an unbiased manner. A biostatistician will develop the randomization plan and will create the un-blinded randomization list to be uploaded to the software. This will enable study personnel to obtain treatment allocations and will provide functionality to manage the treatment allocation process. Furthermore, this enables study team members to maintain identifying information from participants. The randomization software will also track study treatment-allocation progress and provide documentation of the treatment assignment.

Randomization at T3 will be done similar to the one at T2.

Due to the nature of the study and its interventions, neither patients nor study staff will be blinded

to patients' treatment assignments.

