### 6.1 Power for explaining treatment effects

Consider a regression model for correlating within-patient improvement (primary: change in PROMIS Pain Interference; secondary: change in PEG, PGIC; many others as exploratory, see below for details) due to one of the 4 main treatments with a phenotypic variable. Using a two-sided test for correlation at 5% significance level we conclude that we will have the power of at least 80% to detect correlations of 0.28 or higher, conservatively assuming the model is applied to one randomized treatment segment with 102 patients. This corresponds to first phase or second phase treatment in one of the 4 treatment groups, and a model based on the light phenotyping target patient group of 408 total. Similar analysis for the smaller subgroup based on 40 patients with available deep phenotyping for a specific treatment and segment shows that correlation of 0.42 or higher will be detectable with 80% power. This is well within reach as evidenced by available literature on the association between treatment effects and phenotype variables. For example, mindfulness and pain responses showed correlations of 0.43-0.51 in prior reported studies. Our previous studies of the association between pain centralization and analgesic responses in knee osteoarthritis showed similar or higher correlations.

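### The T3 allocation is not spelled out for three treatment-dependent options, and 40 deep-phenotyped patients per treatment is an expected number that the unstratified T2 list does not secure

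*SAP*

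**What the plan says.** SAP 5.5 describes the T2 schedule in two statements: "Block size will be randomized between 4 and 8 and the ordering of treatment assignments within a block will be random" and "Randomization will be performed without stratification". For the second randomisation it has one sentence: "Randomization at T3 will be done similar to the one at T2". It gives no T3 block size, list structure or allocation ratio.

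SAP 5.1 fixes what T3 must do. Patients who still qualify are "re-randomized to receive one of the three treatments they did not receive in the first treatment period". SAP 5.4.2 adds a complication: "Individuals must be willing and eligible to be randomized to receive at least three of the four proposed treatments". A patient eligible for only three treatments has three options at T2 and may have two at T3. Protocol 8.1, which covers both randomisations, says that allocation probabilities will allow for such patients. It gives no algorithm, and SAP 5.5 does not repeat the provision.

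For deep phenotyping, SAP 6.1 bases its power statement on a "smaller subgroup based on 40 patients with available deep phenotyping for a specific treatment and segment", which is 160/4. SAP 6 draws these patients from the randomised target group. Neither document says how the 160 are to be spread over the four arms.

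**The concern.** Two things in SAP 5.5 do not match what the rest of the plan needs.

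**T3.** Equal allocation over three options needs blocks divisible by 3, and neither 4 nor 8 is. A four-treatment list reused at T3 would name the treatment already received in about a quarter of its slots. If those slots are skipped on one list shared by all patients, balance within each first-treatment group is no longer controlled. The T3 allocation determines the stage-2 data that enter the joint T3/T4 model (SAP 9.1.1) and the 12 embedded regimens (SAP 11).

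**T2.** Each deep hypothesis in SAP Table 3 is tied to one treatment. If chance leaves one arm short of deep patients, a surplus in another arm does not restore power for the short arm's hypotheses. The stated 80% therefore describes an arm of exactly 40, which the schedule does not secure.

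**Working it through.** **Inputs from the documents.** 408 randomised at T2, 102 per arm (SAP 5.5, 5.4.1); 160 deep patients (SAP 5.2); 40 per treatment, r = 0.42, two-sided 5%, power 80% (SAP 6.1).

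**Assumptions.** The 160 fall at random among the 408. Between 76 and 102 patients per first treatment are re-randomised at T3. The documents give neither the spread nor the re-randomisation rate.

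**1. The plan's own figure.** Power for a correlation, by Fisher z with bias term and a t-based critical value:

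power ≈ Φ{(z_r − z_c)·√(n − 3)}, with z_r = atanh(r) + r/(2(n − 1)) and z_c = atanh(r_c), where r_c is the critical correlation on n − 2 df.

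At n = 40: z_r = 0.4531, z_c = 0.3228, √37 = 6.083, so (0.1303)(6.083) = 0.793 and power = 0.786. Simulation of the t test gives 0.790, noncentral t 0.814 and plain Fisher z 0.777. The stated 80% is reproduced to within about 2 points. For a like-for-like comparison, the figures below use the 0.786 method.

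**2. Deep patients per arm without stratification.** The number in one arm is hypergeometric:

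- mean = 160 × 102/408 = 40
- SD = √[160 × 0.25 × 0.75 × (408 − 160)/407] = 4.28
- 95% range 32 to 48
- probability that a given arm has fewer than 40: 0.46
- probability that all four arms have exactly 40: 0.001

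The smallest of the four arms averages 35 (95% range 29 to 39). It is 35 or fewer in 54% of draws and 32 or fewer in 15%.

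**3. Power at those sizes (r = 0.42).**

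| Deep patients in arm | Power |
|---|---|
| 32 | 0.69 |
| 35 | 0.73 |
| 40 | 0.79 |
| 45 | 0.83 |
| 48 | 0.86 |

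At n = 35, for example, (0.4539 − 0.3471)·√32 = 0.604, which gives 0.727. Averaged over all arms, power is 0.782, against 0.786 with exactly 40 in each. With T2 blocks of 4 and 8 kept within the deep stratum, the smallest arm is 39 or 40 (power 0.775 to 0.786).

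**4. T3 sequences.** There are 4 first treatments × 3 remaining treatments = 12 cells. Two schemes were simulated: one shared list of four-treatment blocks of 4 and 8, skipping slots that name the treatment already received; and the same blocks kept as a separate list per first treatment.

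| Re-randomised per first treatment | Balanced cell | Smallest cell, shared list | Smallest cell, list per first treatment |
|---|---|---|---|
| 76 | 25.3 | about 20 | about 25 |
| 91 | 30.3 | about 24 | about 30 |
| 102 | 34.0 | about 28 | about 33 |

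**5. What the T3 imbalance costs.** Under the shared list, the mean of 1/n over the 12 cells exceeds its balanced value by 1.5% to 2.0%. The average variance of a contrast between second treatments, adjusted additively for first treatment, rises by 0.9% to 1.2%. The loss is therefore about 1-2% in variance.

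**The case against.** The strongest reply is that SAP 5.5 says T3 is similar to T2, not identical, and leaves the randomisation plan to a biostatistician. Protocol 8.1 already foresees adjusted probabilities for patients with three options. Removing one treatment from a four-treatment block of 4 or 8 leaves a balanced block of 3 or 6 over the other three, so a list per first treatment gives almost perfect balance, as step 4 shows. All of this stands. A reader might infer that the plan cannot generate the T3 allocation. The documents do not support that: they leave the algorithm unstated, and only the shared-list reading loses balance.

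A reader might also infer that the trial will not deliver 40 deep patients per treatment. That is not supported either. Forty is the expected count, some arms will exceed it, and average power hardly moves. The documents do not exclude filling deep places by treatment; Protocol 10 puts the first deep visit after T2 and before Treatment 1.

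Unequal T3 cells matter less than their size suggests. The primary endpoint is the T2 to T3 change, T4 data are added for efficiency with a fallback to stage 1 only, and the regimen analysis is exploratory.

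What the reply does not answer is that the stated rule is no stratification, that no T3 list structure is given, that the restricted-eligibility provision is absent from SAP 5.5, and that nothing in either document ties the deep subset to 40 per arm.

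**Conclusion.** The point holds as a cheap improvement. It does not show a flaw that threatens the primary analysis.

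- **T3:** on a literal shared-list reading, the smallest of the 12 sequences averages about 20 to 28 patients against 25 to 34 if balanced, at a variance cost of about 1-2%. This rests on the assumed 76 to 102 re-randomised per first treatment.
- **Deep subset:** 40 per treatment is expected and not guaranteed. The smallest arm averages 35, where power for r = 0.42 is about 0.73 against about 0.79 at 40; averaged over arms, the loss is 0.004. This rests on an assumed random spread of the 160.

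For scale, losing 15% of deep patients, the ceiling that SAP 7.4 expects for missing data, would take 40 to 34 and power to 0.71. That is about as much as the chance imbalance costs the smallest arm, and stratification would not prevent it.

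**What to change.** - **T2:** stratify the list by agreed deep participation (yes/no), keeping blocks of 4 and 8 within each stratum. If that is not wanted, state deep power over a range of about 32 to 40 patients per arm.
- **T3:** specify a separate list for each first treatment, with blocks of 3 and 6 over the remaining treatments.
- **Restricted eligibility:** carry the Protocol 8.1 provision into SAP 5.5 for both T2 and T3, with the allocation rule written out. Patients with three options do not fit four-treatment blocks at T2, and those left with two do not fit blocks of 3 and 6 at T3.

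The cost is a new list specification from the statistician, and agreement to deep phenotyping must be recorded before the T2 allocation is drawn. No additional patients or visits are needed.

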## 5.6 Study Assessments

Table 1 shows the schedule of assessments for screening, demographic data, outcomes, and light and deep phenotyping. Measurements at T2-T5 may occur within a target observation window around each nominal study sample time ( $\pm 2$  weeks). A subset of 160 eligible subjects enrolled in the clinical trial will undergo deep phenotyping.

# Statistical Analysis Plan

Table 1 Schedule of Assessments

	Scheduled												Unscheduled Visits					
	Pre-screening (-30days)	Study Visit T1 (Week 1)	Ecological Momentary Activity (EMA)-1 (Week 1)	Study Visit T2 (Week 6)	Deep Visit 1 * (Week 6)	Ecological Momentary Activity (EMA)-2 (Week 6)	Intervention 1 (Weeks 7-14)	Study Visit T3 (Week 15)	Deep Visit 2 * (Week 15)	Ecological Momentary Activity (EMA)-3 (Week 15)	Intervention 2 (Weeks 116-23)	Study Visit T4 (Week 224)	Ecological Momentary Activity (EMA)-4 (Week 24)	Ecological Momentary Activity (EMA)-5 (Week 36)	Study Visit T5 (Week 36)	10 Mini-assessments (Weeks 3, 8, 10, 17, 21, 26, 28, 30, 32, 34)	1 Expanded Mini-assessment (Week 12)	1 Mediation Mini-assessment (Week 19)
EMR Eligibility Review	x																	
Screening Eligibility Review	x	x																
Informed Consent		x																
Charlson Comorbidity Index (CCI)		x																
Demographics	x																	
Medical History and Medications	x		x				x				x			x				
Vitals, Height & Weight	x		x				x			x			x					
Biomechanical, Physical Exam & Physical Function Measures																		
2-Minute Walk Test (2MWT)		x		x			x			x		x		x				
4-Meter Walk Gait Speed Test (from SPPB)																		
Timed Sit-to-Stand (STS)																		

## Statistical Analysis Plan

Neurotesting-Patellar Deep Tendon Reflex	x					b			b										
Neurotesting-Achilles Deep Tendon Reflex	x					b			b										
Neurotesting-Sensation	x					b			b										
Neurotesting-Ankle Dorsiflexion (L4)	x					b			b										
Neurotesting-Great toe extension (L5)	x					b			b										
Neurotesting-Hamstrings (S1/S2)	x					b			b										
Neurotesting- Single Leg Calf Raises (S1/S2)	x					b			b										
Neural Tension- Passive Straight Leg Raise + Tightness	x					b			b										
Cross Straight Leg Raise	x					b			b										
SI Provocation- Compression	x					b			b										
SI Provocation- FABER Test	x					b			b										
Fortin Test	x																		
Neurotesting-Hip flexion (L2/L3)						b			b										
Neurotesting-Quadriceps (L3/L4)						b			b										
Neurotesting-Seated Slump Test with Active Straight Leg Raise (ASLR)						b			b										

## Statistical Analysis Plan

Neurotesting- Beighton Score (Pinky, Thumb & Elbow)					b			b											
Neurotesting- Beighton Score (Knees & Hands to floor)					b			b											
Hip Abduction- Dynamometer					b			b											
SI Provocation- Distraction					b			b											
SI Provocation-Thigh Thrust					b			b											
SI Provocation- Gaenslen's					b			b											
SI Joint- Active Straight Leg Raise					b			b											
SI Provocation-Sacral Thrust					b			b											
Hip Extension Dynamometer					b			b											
Lumbar Segmental Mobility (PA Spring Test)					b			b											
Prone Instability Test					b			b											
Inclinometer- Flexibility- Flexion, Extension and Side bending					b			b											
Observation for Aberrant Motion					b			b											
Directional Preference- Repeat flexion, extension, side glide					b			b											

## Statistical Analysis Plan

Hip Provocation- FADDIR						b				b										
Pain Provocation- Quadrant Test						b				b										
Pheno Device- Motion Assessments & Spine Kinematics Data	x																			
Biospecimen Collection																				
Whole blood	x																			
Blood Serum																				
RNA PAXgene																				
Saliva																				
Urine Pregnancy Test	x		x	x		x		x		x	x							x		
Imaging- MRI of Back and Pelvis	x																			
Questionnaire Data																				
Pain Duration and Frequency (cLBP)- 2 Items from NIH Research Task Force Minimum Dataset*	x			x			x			x							x			
Pain location- Radicular Pain Questions Adapted from NIH Research Task Force Minimum Dataset*	x			x				x									x			
Pain Somatization- Abbreviated Pain Somatization Adapted from NIH Research Task	x		x			x			x								x			

## Statistical Analysis Plan

Force Minimum Dataset*																				
Low Back Pain-Specific Pain Intensity*		X		X	X			X	X			X			X	X	X	X	X	X
Opioid use- Single-Item Current Opioid Use*		X		X	X			X	X			X			X		X			
Pain Intensity (PEG)*		X			X				X			X			X		X			
PROMIS Physical Functioning 6b*		X		X	X			X	X			X			X	X	X	X		
PROMIS Anxiety 4a*		X		X	X			X	X			X			X	X	X	X		
PROMIS Depression-4		X		X	X			X	X			X			X	X	X	X		
PROMIS Fatigue		X		X	X			X	X			X			X	X	X	X		
PROMIS Sleep Disturbance 6a*		X		X	X			X	X			X			X	X	X	X		
Sleep Duration*		X		X	X			X	X			X			X	X	X	X		
PROMIS Social Role Activity		X		X				X				X			X	X	X	X		
PROMIS Pain Interference 4a*	X	X		X	X			X	X			X			X	X	X	X	X	X
PROMIS Cognitive Function		X		X	X			X	X			X			X	X	X	X		
PROMIS Pain intensity		X		X	X			X	X			X			X	X	X	X	X	X
Pain Catastrophizing Scale (PCS)*		X		X	X			X	X			X			X		X			
Patient Health Questionnaire-2 (PHQ-2)*		X			X				X								X			

## Statistical Analysis Plan

Generalized Anxiety Disorder-2 (GAD-2)*	x			x				x							x			
Patient global impression of change (PGIC)/Global Rating of change (GROC)*				x	x		b	x	x		b	x			x	x	x	x
Tobacco, Alcohol, Prescription medication, and other Substance use (TAPS)*	x				x				x						x			
Fibromyalgia (FM) Survey Criteria 2016 (Widespread Pain Index (WPI) and Symptom Severity Index (SSI))	x		x				x				x			x	x	x		
Widespread Pain*	x			x				x							x			
Life Orientation Test-Revised (LOT-R)	x		x				x				x			x				
Chronic Overlapping Pain Conditions Screener (COPCS)	x			x				x										
Pain Self-efficacy Questionnaire (PSEQ)	x		x				x				x			x				
PainDETECT	x		x	x			x	x			x			x				
Oswestry Disability Scale (ODI)	x		x			b	x			b	x			x				
Chronic Pain Acceptance Questionnaire (CPAQ-8)	x		x			c	x			c	x			x				
Fear Avoidance Beliefs Questionnaire (FABQ+Physical Activity)	x		x			x				x				x	x	x		

## Statistical Analysis Plan

Experiences Questionnaire (EQ)-11	x		x				x			x			x		x	x	
Experiences Questionnaire (EQ)-5							c			c							
Perceived Stress Scale (PSS)	x		x				x			x			x				
Positive and Negative Affect Scale (PANAS)	x		x				x			x			x				
Childhood and Recent Traumatic Events Scale (CTES)	x																
Credibility and Expectancy Questionnaire (CEQ)			x				x			x			x				
Client Satisfaction Questionnaire (CSQ)	x		x				x			x			x				
HEAL Treatment Expectancy v1.0 Short Form 6a	x		x				x			x			x				
Numeric Pain Rating Scale (NPRS)	x	x		x	x	b		x	x	b		x	x				
General Sensory Sensitivity (GSS-8)	x		x	x			x	x		x			x	x	x	x	
Ecological Momentary Activity (EMA) Mental and Physical Symptoms		x			x			x			x	x					
Low-Back Pain Treatment Categories Questionnaire	x		x				x			x				x	x		
Patient Preference Questionnaire	x																

## Statistical Analysis Plan

Patient Outcome Questionnaire	x																			
BACPAC Customer Service Questionnaire							x								x					
Randomization			a				A													
Adverse Event Reporting	x	x	x	x	x	x	X	x	x	x	X	x	x	X	x	x	x	x	x	x
Deep Phenotyping Participants (n=160)																				
Biospecimen					x			x											x	
RNA PAXgene																			x	
Blood Serum																				x
Whole Blood																				
Neuroimaging- fMRI				x				x											x	
Conditioned Pain Modulation (CPM) Test				x				x											x	
Cuff Ascending and Pseudorandom				x				x											x	
Multimodal Automated Sensory Test (MAST) and Cuff Familiarization				x				x											x	
Multimodal Automated Sensory Test (MAST) Ascending				x				x											x	
Temporal Summation				x				x											x	
Tonic Cuff				x				x											x	
Two Point Discrimination Test (TPDT)				x				x											x	
Visual task				x				x											x	

# Only completed for deep phenotyping (n=160) participants

\* Part of the HEAL minimum data set

a Randomization will only occur if PGIC $\geq$ 2

## Statistical Analysis Plan

*b Occurs if intervention is Physical Therapy*

*c Occurs if intervention is MBSR*

## 6 Sample Size

The study aims to continue randomizing patients with cLBP to initial treatment until 102 randomized patients per group are available for the analysis (i.e. completed their T1-T4 visits and had PGIC $\geq$ 2 at T2). This is the target patient group. Based on assumed attrition rates we expect the total number of consented patients to be over 500. Attrition rates include patients who are not randomized because their pain was “very much improved” after run-in (PGIC=1 at T2). Such patients will still be included in the analysis with their limited data. The power analysis, however, excludes these patients because effects in the randomized participants are of primary interest. The smaller subgroup based on 40 patients will be from the target patient group for deep phenotyping for specific treatments.

### 6.1 Power for explaining treatment effects

Consider a regression model for correlating within-patient improvement (primary: change in PROMIS Pain Interference; secondary: change in PEG, PGIC; many others as exploratory, see below for details) due to one of the 4 main treatments with a phenotypic variable. Using a two-sided test for correlation at 5% significance level we conclude that we will have the power of at least 80% to detect correlations of 0.28 or higher, conservatively assuming the model is applied to one randomized treatment segment with 102 patients. This corresponds to first phase or second phase treatment in one of the 4 treatment groups, and a model based on the light phenotyping target patient group of 408 total. Similar analysis for the smaller subgroup based on 40 patients with available deep phenotyping for a specific treatment and segment shows that correlation of 0.42 or higher will be detectable with 80% power. This is well within reach as evidenced by available literature on the association between treatment effects and phenotype variables. For example, mindfulness and pain responses showed correlations of 0.43-0.51 in prior reported studies. Our previous studies of the association between pain centralization and analgesic responses in knee osteoarthritis showed similar or higher correlations.

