## 9 Analysis Plan

### 9.1 Objective 1 Analysis Plan

**Objective 1:** Assess differential treatment response using the light and deep phenotype data. The main hypotheses of Objective 1 will be addressed by fitting a joint regression model the primary pain outcome (PROMIS pain interference score) at time point T3 which gains efficiency by incorporating observations at time point T4. The purpose of this analysis is to demonstrate that clinical measures are capable of predicting differential responsiveness to the four cLBP treatments. This analysis will assess the degree to which the clinicians' hypothesized treatment modifiers predict differential treatment response. Testing the differential treatment response hypotheses will be handled by including treatment-phenotype interactions in the model. The analysis will be repeated for the secondary pain outcomes (Pain intensity (PEG) and Patient Global Impression of Change (PGIC)).

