We will fit the model for all repeated measures ( $Y_{3i}, Y_{4i}$ ) using generalized estimating equations (GEE) with a working independence covariance matrix through the R package *gee*. We will use robust standard errors for variance estimation to account for the use of repeated measures. Prior to conducting inference, we will assess the functional forms of the predictors and the validity of the assumptions required for joint stage modeling, especially the assumption of constant interaction effects across treatment stages. If the assumptions for joint modeling are violated, we will conduct the primary analysis with stage 1 data only. For inference, we additionally assume  $Y_{3i}, Y_{4i}$  follow a multivariate normal distribution.

The clinical objective of Aim 1 is to show that patient responsiveness to treatment depends on their

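### SAP 6.1 gives 80% power for a correlation within one arm, but the primary test is a treatment-by-phenotype interaction: on the same one-segment basis it has about 70% power (light) and 50–66% (deep)

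*SAP*

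**What the plan says.** SAP 6.1 describes a regression of within-patient improvement on one phenotypic variable. The claim for the light measures is "power of at least 80% to detect correlations of 0.28 or higher, conservatively assuming the model is applied to one randomized treatment segment". The test is specified as "Using a two-sided test for correlation at 5% significance level", "applied to one randomized treatment segment with 102 patients". The scope is explicit: "This corresponds to first phase or second phase treatment in one of the 4 treatment groups". For deep phenotyping the basis is a "smaller subgroup based on 40 patients with available deep phenotyping for a specific treatment and segment", where a "correlation of 0.42 or higher will be detectable with 80% power". Protocol 18.1.5 has the same kind of statement with slightly different inputs (r = 0.3 with 100 patients; r = 0.43 with 40).

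The analysis sections describe a different test. SAP 9.1 states: "Testing the differential treatment response hypotheses will be handled by including treatment-phenotype interactions in the model". SAP 9.1.1 fits all four arms together, with main effects of treatment and of each phenotype. It applies a two-sided Wald test to each interaction coefficient and rejects at |W| ≥ 2, using robust standard errors. The default fit pools T3 and T4 and takes the interactions to be the same in both stages. The fallback is: "If the assumptions for joint modeling are violated, we will conduct the primary analysis with stage 1 data only". SAP 9.1.2 carries the same inference over to the deep measures in one model; its Table 5 lists 15 terms.

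**The concern.** A within-arm correlation asks whether a phenotype tracks improvement among patients given one treatment. It cannot separate a predictor of response to that treatment from a general prognostic factor. The interaction asks whether the slope in the named arm differs from the common slope in the arms that do not carry that interaction. Because the reference slope is also estimated, the variance is larger: with three equal reference arms it is about 4/3 of the one-arm variance.

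Differential response is the trial's main question. A reader who meets a null interaction will judge it against the 80% in 6.1, a figure calculated for another test. This matters most if the joint-model assumptions fail and stage 1 alone is used, because the analysis then rests on the single segment that 6.1 takes as its basis.

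**Working it through.** **Inputs from the documents.** Two-sided 5% level; r = 0.28 with 102 per arm; r = 0.42 with 40 per arm; four equal arms (408 and 160 in total). The 102 are counted after attrition, so no dropout adjustment is applied.

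**Assumptions not in the documents.** Zero correlation in the other arms; covariates that explain no outcome variance. Both are varied in step 4.

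**1. The plan's own figures (within-arm correlation).** Fisher z: power = Φ(atanh(r)·√(n−3) − 1.96).
- Light: atanh(0.28) = 0.2877; √99 = 9.950; Φ(2.862 − 1.96) = 81.7% (exact bivariate normal 82.0%). The stated figure holds.
- Deep: atanh(0.42) = 0.4477; √37 = 6.083; Φ(2.723 − 1.96) = 77.7%. Other methods give 78.7% (bias-corrected), 78.8% (exact) and 81.4% (noncentral t with fixed predictor). The stated 80% is within method-to-method variation.

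**2. Interaction, one segment, one phenotype.** Power = Φ(atanh(r)/SE − 1.96), with SE = √(1/(n−3) + 1/(m−3)) and m the number of patients in the reference arms.
- Light, 102 against 306: SE = √(1/99 + 1/303) = 0.1158; 0.2877/0.1158 = 2.485; power 70.0% (68.6% at the SAP's |W| ≥ 2). Slope formulas and simulation give 69–72%. For 80%: tanh(2.80 × 0.1158) = 0.31, or 0.32 at |W| ≥ 2.
- Fibromyalgia score: SAP Table 2 pairs it with both acupressure and duloxetine, so only two arms form the reference. SE = √(1/99 + 1/201) = 0.1228; power 64.9%. Simulation of the full light model gives 66.5%.
- Deep, 40 against 120: SE = √(1/37 + 1/117) = 0.1886; 0.4477/0.1886 = 2.374; power 66.0% (63–72% across methods). For 80%: tanh(2.80 × 0.1886) = 0.48, or 0.49 at |W| ≥ 2.

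**3. The full models.**
- Light: 8 interactions + 7 phenotype main effects + 4 arms + about 8 covariate terms = about 27 parameters on 408 patients. Simulated power with the robust Wald test is about 70%.
- Deep: 15 + 15 + 4 + about 8 = about 42 parameters on 160 patients. An ordinary t test, which holds its size, gives about 50–58%; the spread depends mainly on the residual-variance assumption. The SAP's robust Wald test gives about 65%, but at this sample size it rejects about 10% of the time under the null, so part of that power is lost type I error control.
- The covariate count depends on how race and education are coded, which the SAP does not say.

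**4. Sensitivity, one segment.**

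| Change | Light, r = 0.28 | Deep, r = 0.42, single measure |
|---|---|---|
| Other arms r = +0.1 | 37% | 45% |
| Other arms r = 0 | 70% | 66% |
| Other arms r = −0.1 | 92% | 83% |

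If the covariates explain 25% of residual variance (an illustrative value), light power by the SAP's test is about 80%. The full deep model reaches about 76% by the same, oversized test.

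**5. Joint T3 and T4 model.** The documents do not give the share f of randomized patients who are re-randomized. Replacing n by n(1 + f) in step 2, and counting each T4 record as an independent observation, gives:

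| f | Light | Deep, single measure |
|---|---|---|
| 0.2 | 78% | 74% |
| 0.5 | 86% | 84% |
| 0.8 | 92% | 90% |

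These are upper guides: the same patients contribute both records, and the model has extra stage-2 terms.

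**The case against.** Several points on the other side have force.

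- **The planned primary analysis is the joint model, not one segment.** This stands. A reader might infer that the trial as planned has only 70% power for its main test. The documents do not support that: stage 1 alone is the fallback, and pooling may bring power to 80% or more. Nor do they support one firm joint figure, since the re-randomized share is not given and equal interactions are an assumption.
- **The word *conservatively* is fair in one sense.** Using one segment instead of two is conservative, and step 5 confirms it. What it does not cover is the change from a correlation to an interaction.
- **The 50–58% for the deep model does not come from the SAP's test.** This is correct, and the figure must be labelled as a size-controlled alternative. The robust Wald figure of about 65% is the SAP's own, but it comes with about 10% rejection under the null.
- **The covariates include the baseline outcome and may well explain variance.** At 25% explained, the light shortfall disappears. The documents give no value, so this belongs in a sensitivity range.
- **Larger correlations are cited.** SAP 6.1 mentions 0.43–0.51 for mindfulness and pain response. At 0.43 the light interaction has about 98% power in one segment (0.4599/0.1158 = 3.97). A single deep measure still needs about 0.48, and the 15-interaction model by t test has about 76% at 0.50.
- **SAP 7.5 already concedes little power for interactions under multiplicity control**, and plans to report intervals and effect sizes. That softens the harm. It gives no power figure for the uncontrolled test actually planned, and 9.1.1 still specifies a rejection rule.

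**Conclusion.** The point holds as a mismatch between the sample-size justification and the primary test. It is not an arithmetic error: a reader might take the 80% in 6.1 to be miscalculated, but the light figure reproduces and the deep one is off by at most about two points on some methods.

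On 6.1's one-segment basis, all the deep figures and the central light figure fall below 80% at the stated correlations. The light shortfall is about 10 points and the single-measure deep shortfall about 14; in the full deep model with a size-controlled test it is 22–30 points. These sizes rest on zero correlation elsewhere and uninformative covariates. The light result is sensitive to both, and either assumption can move it to 80% or above. The deep result is less easily rescued, because the planned model is large for 160 patients.

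**What to change.** Restate SAP 6.1 for the interaction test:

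1. Keep the within-arm correlation figures if wanted, but label them as such.
2. Give one-segment interaction power with its assumptions: light about 70% at r = 0.28 (about 65–67% for the fibromyalgia terms), with 80% at about 0.31–0.32; deep at r = 0.42 about 66% for a single measure, with 80% at about 0.48–0.49.
3. For the planned 15-interaction deep model, give about 50–58% with a size-controlled test, and note that the robust Wald test gives about 65% with about 10% rejection under the null.
4. Show sensitivity to the correlation in the other arms and to the variance that the covariates explain.
5. Report joint T3 and T4 power separately, as a range over the re-randomized share, conditional on equal interactions in both stages.
6. Keep *conservatively* only for the use of one segment instead of two, and say that it does not describe the choice of test.

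The cost is SAP wording and less favourable stated figures. Sample size, design and data collection do not change.
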